13.0 SAFETY REPORTING

13.1 Definitions:

Adverse event (AE) means any untoward medical occurrence in a patient or subject administered a medicinal product; the untoward medical occurrence does not necessarily have a causal relationship with this treatment. An AE can therefore be any unfavorable and unintended sign (including an abnormal laboratory finding), symptom, or disease temporally associated with the use of a medicinal (investigational) product whether or not it is related to the medicinal product. This includes any newly occurring event, or a previous condition that has increased in severity or frequency since the administration of study drug.

An abnormal laboratory value will not be assessed as an AE unless that value leads to discontinuation or delay in treatment, dose modification, therapeutic intervention, or is considered by the investigator to be a clinically significant change from baseline.

An adverse drug reaction (ADR) is a response to a medicinal product which is noxious and unintended. Response in this context means that a causal relationship between a medicinal product and an adverse event is at least a reasonable possibility. This includes adverse reactions which arise from: use of a medicinal product within the terms of the marketing authorization; use outside the terms of the marketing authorization, including overdose, misuse, abuse and medication errors; and occupational exposure*.

* This corresponds to the exposure to a medicinal product for human use as a result of one's occupation, such as nurses who may handle products routinely in their occupational setting.

Adverse Events will be reported in accordance with all 21 CFR 312.32 requirements" (https://www.accessdata.fda.gov/scripts/cdrh/cfdocs/cfcfr/cfrsearch.cfm?fr=312.32)

Medically attended AEs

MAEs will be collected during the 6 months after vaccination. Medically attended AEs are defined as AEs leading to a visit to or from medical personnel for any reason. A phone call with a healthcare professional was not considered medically attended.

Participants will be asked about any AE at FU1, V2, and V3. Research coordinators will interview all participants at these visits and ask them about any AE since immunization.

Serious adverse Event.

An adverse event is considered "serious" if, in the view of either the investigator or sponsor, meets any of the following criteria:

- Results in death
- Are life-threatening (Refers to an AE in which the subject was at risk of death at the time
 of the event. It does not refer to an event, which hypothetically, might have caused death
 if it were more severe.)
- Requires an inpatient hospitalization or prolongation of an existing hospitalization

- Results in persistent or significant disability or incapacity. (Disability is defined as a substantial disruption of a person's ability to conduct normal life functions.)
- Results in a congenital anomaly/birth defect, constitute, based upon appropriate medical
 judgment, an event that may jeopardize the subject's health and may require medical or
 surgical intervention to prevent one of the other outcomes listed above.
- Important medical events that may not result in death, be life-threatening, or require hospitalization and that may be considered serious when, based upon appropriate medical judgment, they may jeopardize the patient or subject and may require medical or surgical intervention to prevent one of the outcomes listed in this definition. (Examples of such medical events include allergic bronchospasm requiring intensive treatment in an emergency room or at home, blood dyscrasias or convulsions that do not result in inpatient hospitalization, or the development of drug dependency or drug abuse")

13.11 Relationship of Adverse Event to Study Vaccine

The relationship or association of the study vaccine in causing or contributing to the AE will be characterized by the investigator as "Related" or "Not Related". All AE, SAE, Adverse of Special interest will be presented in a summary table. If the relationship information is missing, the AE will be considered "Related" in the summary but will be presented as missing in the data listings.

We will use a binary scale related versus not related. We will use the following definitions:

- **Not related**: There is not a reasonable possibility of relationship to study vaccine. The AE does not follow a reasonable temporal sequence from administration of study vaccine or can be reasonably explained by the subject's clinical state or other factors (eg, disease under study, concurrent diseases, and concomitant medications).
- **Related:** There is a reasonable possibility of relationship to study vaccine. The AE follows a reasonable temporal sequence from administration of study vaccine and cannot be reasonably explained by the subject's clinical state or other factors (e.g., disease under study, concurrent diseases, or concomitant medications), represents a known reaction to study vaccine or other vaccines in its class, is consistent with the known pharmacological properties of the study vaccine, and/or resolves with discontinuation of the study vaccine(and/or recurs with re-challenge, if applicable).

13.2 Severity of Event

All AEs will be assessed by the principal investigator using the Table below.

The intensity of the following solicited AEs will be assessed as described:

Table Intensity scales for AEs

Table Intensity scales		Danamatan
Event	Intensity grade	Parameter
Pain at	0	None
administration	1	Mild: Any pain neither interfering with nor
site	0	preventing normal everyday activities.
	2	Moderate: Painful when limb is moved and
	-	interferes with everyday activities.
	3	Severe: Significant pain at rest. Prevents normal
	4	everyday activities.
	4	Potentially life threating: Emergency room (ER)
Dada a a at a day	!!	visit or hospitalization
Redness at adm		Greatest surface diameter in mm (see below)
Swelling at admi	nistration site	Greatest surface diameter in mm (see below)
Temperature*	T	Temperature in °F (see below)
Pruritis at	0	None
administration	1	Mild: Itchy sensation that neither interferes with
site		nor prevents normal everyday activities.
	2	Moderate: Itchy sensation that interferes with
		normal everyday activities.
	3	Severe: Itchy sensation that prevents normal
		everyday activities.
	4	Potentially life threating: ER visit or
		hospitalization
Headache	0	None
	1	Mild: Headache that is easily tolerated
	2	Moderate: Headache that interferes with normal activity
	3	Severe: Headache that prevents normal activity
	4	Potentially life threating: ER visit or
		hospitalization
Fatigue	0	None
	1	Mild: Fatigue that is easily tolerated
	2	Moderate: Fatigue that interferes with normal
		activity
	3	Severe: Fatigue that prevents normal activity
	4	Potentially life threating: ER visit or
		hospitalization
Myalgia	0	None
	1	Mild: Myalgia present but does not interfere with
		activity
	2	Moderate: Myalgia that interferes with normal
	_	activity
	3	Severe: Myalgia that prevents normal activity
	1	1

Event	Intensity grade	Parameter
	4	Potentially life threating: ER visit or
		hospitalization
Arthralgia	0	None
	1	Mild: Arthralgia present but does not interfere with activity
	2	Moderate: Arthralgia that interferes with normal activity
	3	Severe: Arthralgia that prevents normal activity
	4	Potentially life threating: ER visit or hospitalization
Gastrointestinal symptoms	0	None
	1	Mild: Gastrointestinal symptoms that are easily tolerated
	2	Moderate: Gastrointestinal symptoms that interfere with normal activity
	3	Severe: Gastrointestinal symptoms that prevent normal activity
	4	Potentially life threating: ER visit or hospitalization
Shivering/chills	0	None
	1	Mild: Shivering that is easily tolerated
	2	Moderate: Shivering that interferes with normal activity
	3	Severe: Shivering that prevents normal activity
	4	Potentially life threating: ER visit or hospitalization
Acute allergio	0	none
event	1	Transient flushing or rash; drug fever <38°C (<100.4°F)
	2	Rash; flushing; urticaria; dyspnea; drug fever ≥38°C (≥100.4°F)
	3	Symptomatic bronchospasm, with or without urticaria; parenteral medication(s) indicated; allergy-related edema/angioedema; hypotension
	4	Anaphylaxis/Death
Syncope	0	None
	1	Pre-syncopal symptoms light headness.
	2	Symptoms without loss of consciousness
	3	Symptoms with loss of consciousness
	4	Life threatening consequences
Paresthesia	0	None

Event	Intensity grade	Parameter
	1	Asymptomatic; loss of deep tendon reflexes or paresthesia (including tingling) but not interfering with function
	2	Sensory alteration or paresthesia (including tingling), interfering with function, but not interfering with ADL
	3	Sensory alteration or paresthesia interfering with ADL
	4	Disabling
Hypoesthesia	0	None
	1	Asymptomatic; altered sensory response (e.g touch, virbtation or cold temperature) but not interfering with function
	2	Sensory alteration, interfering with function, but not interfering with ADL
	3	Sensory alteration interfering with ADL
	4	Disabling

^{*}Fever is defined as temperature ≥ 38.0°C (100.4°F) by any route. The preferred location for measuring temperature will be the oral route.

The maximum intensity of injection administration site redness/swelling and fever will be graded as follows:

	Redness/swelling	Fever
0:	≤20 mm	<38.0°C (100.4°F)
1:	>20 - ≤50 mm	≥38.0°C (100.4°F) - ≤38.5°C (101.3°F)
2:	>50 - ≤100 mm	>38.5°C (101.3°F) - ≤39.0°C (102.2°F)
3:	>100 mm	>39.0°C (102.2°F)
4	Necrosis or exfoliative dermatitis	Fever resulting in hospitalization

The investigator will assess the maximum intensity that occurred over the duration of the event for all unsolicited AEs (including SAEs) recorded during the study. The assessment will be based on the investigator's clinical judgement.

The intensity should be assigned to 1 of the following categories:

Grade	
1 (mild)	An AE which is easily tolerated by the participant, causing minimal discomfort and not interfering with everyday activities.
2 (moderate)	An AE which is sufficiently discomforting to interfere with normal everyday activities.

3 (severe)	An AE which prevents normal, everyday activities. Such an AE would, for example, prevent attendance at work/school and would cause the participant to seek medical advice.
4 (potentially life threating)	An AE which results in an emergency room visit or hospitalization

An AE that is assessed as Grade 3 (severe) should not be confused with an SAE. Grade 3 is a category used for rating the intensity of an event; and both AEs and SAEs can be assessed as Grade 3. An event is defined as 'serious' when it meets 1 of the pre-defined outcomes as described in the section above.

Clarification should be made between a serious AE (SAE) and an AE that is considered severe in intensity (Grade 3 or 4) because the terms serious and severe are NOT synonymous. The general term severe is often used to describe the intensity (severity) of a specific event; however, the event itself may be of relatively minor medical significance (such as a Grade 3 headache). This is different from serious, which is based on the patient/event outcome or action criteria described above, and is usually associated with events that pose a threat to a patient's life or ability to function. Severe AE (grade 3 or 4) do not necessarily need to be considered as serious. For example, a white blood cell count of 1000/mm³ to less than 2000 is considered Grade 3 (severe) but may not be considered serious. Seriousness (not intensity) serves as a guide for defining regulatory reporting obligations.

13.21 Adverse Events of Special Interest

Myocarditis and pericarditis will be adverse events of special interest. All patients will be counseled on the potential risk of myocarditis or pericarditis from COVID-19 vaccination.

- 1) Potential myocarditis and pericarditis events
- a. Participants reporting acute chest pain, shortness of breath, palpitations, or other signs or symptoms of myocarditis or pericarditis within 4 to 6 weeks after vaccination must be referred to a cardiologist for evaluation and management.
- b. Cases of myocarditis and pericarditis will be followed until resolution of symptoms and abnormal test findings.

Myocarditis and pericarditis cases will be defined by based on the Centers for Disease Control and Prevention (CDC) care definition. ²³ (Appendix 5)

- 2) IBD flares will be evaluated based on SCAI, PDAI, and SCCAI based on follow-up at V1, V2, & V3..
- 3) Solid organ transplant rejection will be reviewed based on follow-up at V1, V2, & V3. Episodes of acute rejection will be documented by chart review.

13.22 Expectedness to Study Intervention

The PI will be responsible for determining whether an AE is expected or unexpected in relation to the study procedures and intervention(s) (as applicable).

An AE will be considered unexpected if the nature, severity, or frequency of the event is not consistent with the risk information previously described in the clinical protocol, device manual, investigator's brochure, the package insert(s), the IRB application, or the informed consent document. Expectedness is recorded for both study procedures and interventions.

13.23 Time Period and Frequency for Event Assessment and Follow-Up

The occurrence of an AE or SAE may come to the attention of study personnel during study visits and interviews of a study subject presenting for medical care, or upon review by a study monitor. All AEs including local and systemic reactions not meeting the criteria for SAEs will be captured on the appropriate CRF. Information to be collected includes event description, time of onset, clinician's assessment of severity, relationship to study product (assessed only by those with the training and authority to make a diagnosis), and time of resolution/stabilization of the event. All AEs occurring while on study must be documented appropriately regardless of relationship. All AEs will be followed to adequate resolution.

Any medical condition that is present at the time that the subject is screened will be considered as baseline and not reported as an AE. However, if the study subject's condition deteriorates at any time during the study, it will be recorded as an AE.

Changes in the severity of an AE will be documented to allow an assessment of the duration of the event at each level of severity to be performed. AEs characterized as intermittent require documentation of onset and duration of each episode.

The PI will record all reportable events with start dates occurring any time after the administration of the study drug through the 6 month follow-up visit. At each study visit, the investigator will inquire about the occurrence of AE/SAEs since the last visit. Events will be followed for outcome information until resolution, stabilization, or completion of study participation.

13.24 Reporting AEs and SAEs

Institution/Investigator is solely responsible for reporting all Adverse Events and Serious Adverse Events to regulatory authorities, investigators, IRBs or IECs, and Novavax, as applicable, in accordance with national regulations in the countries where the study is conducted.

13.24.1 Reporting AEs

- AEs will be recorded from the initiation of study treatment until the 6 month follow-up visit.
- AEs will be recorded regardless of whether they are considered related to the study drug(s).
- All AEs will be recorded on the appropriate study specific eCRF form within <the clinical trial management system>.
- All AEs considered related to the vaccine will be followed until resolution to ≤ Grade 1 or baseline, deemed clinically insignificant, and/or study completion.

13.24.2 Reporting of SAEs

The sponsor-investigator will immediately review all SAEs, whether or not considered study intervention-related, including those listed in the protocol or package insert and will provide an assessment of whether there is a reasonable possibility that the study intervention caused the event.

All SAEs will be followed until satisfactory resolution or until the sponsor-investigator deems the event to be chronic or the subject is stable. Other supporting documentation of the event may be requested by the Data Coordinating Center (DCC) should be provided as soon as possible.

The sponsor-investigator will be responsible for notifying the FDA of any unexpected fatal or life-threatening suspected adverse reaction as soon as possible, but in no case later than 7 calendar days after the sponsor's initial receipt of the information. In addition, the sponsor-investigator must notify FDA and all participating investigators in an Investigational New Drug (IND) safety report of potential serious risks, from clinical trials or any other source, as soon as possible, but in no case later than 15 calendar days after the sponsor determines that the information qualifies for reporting.

13.24.3 Additional Reporting Requirements

Regardless of expectedness or causality, all must also be reported in English by a facsimile to Novavax or a designee:

Adverse Event Reporting. Investigator shall report all Adverse Events ("AEs"), including follow-up information, as defined below, concerning a Novavax Product directly to Novavax by emailing [contact] in the form of a CIOMS I Form or electronic AE Data Capture Form:

- o within one (1) Business Day of receipt/awareness of a Serious Adverse Event (SAE), as defined below;
- o within three (3) Business Days of receipt/awareness of an AEs.

On a monthly basis, Investigator will provide a listing of all AEs sent to Novavax [contact] for the previous month. The reconciliation list should be provided no later than the 15th of the month for the previous month. Any discrepancy identified during reconciliation shall be investigated, clarified, and agreed upon by both parties.

Novavax shall be solely responsible for reporting of Adverse Event information to regulatory authorities, which shall include reporting of individual Adverse Events and periodic safety reports.

"Adverse Event" means any untoward medical occurrence in a patient or clinical trial subject administered a medicinal product and which does not necessarily have a causal relationship with this treatment. An AE can therefore be any unfavorable and unintended sign (e.g., an abnormal laboratory finding), symptom, or disease temporally associated with the use of a medicinal product, whether or not considered related to the medicinal product. This includes other safety information such as:

- o Overdose, abuse, or misuse of the product;
- o An adverse event occurring from the withdrawal of the product;
- Lack of product effect/efficacy;
- o Accidental exposure;
- o Medication error (i.e., administration of expired product)
- o Pregnancy or exposure during breast feeding:
- o Suspected transmission of infectious agents;
- o An unexpected therapeutic or clinical benefit;
- o Off label use.

"Serious Adverse Event" means any untoward medical occurrence that, at any dose,

- o results in death;
- o is life-threatening;
- o requires inpatient hospitalization or prolongation of an existing hospitalization;
- o results in persistent or significant disability or incapacity;
- o is a congenital anomaly/birth defect; or
- o is a medically important event or reaction.

Fatal and Life-Threatening SAEs within 1 business day of the sponsor-investigator's observation or awareness of the event

All other serious (non-fatal/non-life threatening) events within 3 business days of the sponsor-investigator's observation or awareness of the event

All reported adverse drug reactions and safety issues related to Novavax will be included in the final study report.

13.25 Unanticipated Problems

An unanticipated problem (UP), as defined by the DHHS Office for Human Research Protection (OHRP), is any incident, experience, or outcome that meets all of the following criteria:

- The incidence, experience, or outcome is unexpected given the research procedures described in protocol-related documents (e.g., the study protocol, the informed consent documents, the Investigator's Drug Brochure) and the characteristics of the subject population being studied. An event may be considered unexpected if it exceeds the nature, severity, or frequency described in the study-related documents, Investigator's Drug Brochure, product labeling, or package insert.
- The incidence, experience, or outcome is related or probably related to participation in the research study. "Probably related" means the incidence, experience, or outcome is more likely than not to be caused by the research study procedures.
- The occurrence of the incidence, experience, or outcome suggests that the research places subjects or others at a greater risk of harm (physical, psychological, economic, or social) than was previously known or recognized.

The investigator will report UPs to the reviewing IRB and to the Data Coordinating Center (DCC). The UP report will include the following information:

- Protocol identifying information: protocol title and number, Pl's name, and the IRB project number;
- A detailed description of the event, incident, experience, or outcome;
- An explanation of the basis for determining that the event, incident, experience, or outcome represents an UP;
- A description of any changes to the protocol, informed consent documents, or other corrective actions that have been taken or are proposed in response to the UP.

Report UPs within the timeframe specified by the IRB of record.

13.26 Safety Oversight and Stopping Rules

To evaluate whether the vaccine results in SAE, IBD flares, transplant rejection, or myocarditis/pericarditis these will be monitored with the following DSMP. For every 40 patients enrolled in the study, the rate of SAE and IBD flares or episodes of acute rejection will be reviewed. SAE will be reviewed based on follow-up at V1, V2, V3, and vaccine diaries. IBD flares will be evaluated based on SCAI, PDAI, and SCCAI, and episodes of acute rejection will be documented by chart review. Episodes of potential myocarditis or pericarditis will be reviewed after evaluation by a cardiologist and defined based on CDC case definition (appendix 5).A The Principal Investigator (PI) will be responsible for reviewing these data will be reviewed continuously and pause the study if any stopping rules are met. He will have the SMC review the AE and determine if study should be stopped.

The study will be halted if any of the following criteria are met:

- Any serious AE occurs, including death, that is assessed as related to the product and occurring within the entire length of the study.
- Three or more participants experience the same or similar grade 3 or greater AEs, including laboratory abnormalities, that are assessed as related to the product, and occurring within the entire length of the study.
- More than 5 participants have an IBD flare of at least moderate activity (defined by the Short Crohn's Disease Activity Index [sCDAI], Simplified Pouchitis Disease Activity Index [PDAI], or the Simple Clinical Colitis Activity Index [SCCAI]) without a known cause.
- More than 4 participants have allograft rejection that requires treatment without a known cause. ²⁴
- More than 2 participants have an episode of myocarditis or pericarditis.

In the event that study stopping rules are met, enrollment and vaccine administration in the study will be paused while an assessment by the Sponsor-Investigator takes place.

Progress reports and notifications of unanticipated problems, adverse events, protocol deviations, and protocol violations will be reported to the IRB per the posted guidance.

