Success Criterion: Descriptive

6.4 Evaluate the disease activity following administration of the booster dose up to 30 days post-vaccination and during the whole post-vaccination follow-up period.

Disease activity will be assessed by monitoring disease activity using the Short Crohn's Activity Index (SCAI)¹⁹ for patients with Crohn's disease or the Simple Clinical Colitis Activity Index (SCCAI) questionnaire for patients with Ulcerative colitis at the baseline visit (V1), V2, and V3 visits. For patients with pouchitis we will use the simplified pouchitis disease activity index (PDAI). The incidence of IBD flares will be evaluated in all patients receiving recombinant boosters. This will be quantified by patients who were in clinical remission who develop a disease flare after receiving a recombinant COVID-19 booster.

Endpoint:

The number and percentage of participants reporting disease flares of IBD.

Success Criterion: Descriptive

6.5 Evaluate for solid organ transplant rejection following administration of booster dose, up to 30 days post-vaccination and during the whole post-vaccination follow-up period.

Participants will be asked if they have been diagnosed with acute rejection after their baseline visit (V1). Episodes of acute rejection will be collected by searching electronic medical records and asking patients at each clinic visit (V2 and V3). Acute rejection will be defined as a notation of a new episode of acute rejection (cellular or antibody-mediated), a steroid bolus and taper in the absence of another indication, or administration of a T or B cell depleting agent or immune globulin.²⁰

This will be quantified by patients who develop acute rejection of their transplant after receiving a recombinant COVID-19 booster.

Endpoint:

The number and percentage of participants reporting acute rejection of their transplant.

Success Criterion: Descriptive

[figure not shown]

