8.5 Premature Subject Discontinuation

Patients will be encouraged to complete the study; however, they may voluntarily withdraw at any time.

The Principal Investigator may discontinue or withdraw a subject from the study for the following reasons at his/her discretion:

- Subject non-compliance with study requirements (e.g., study intervention non-compliance, do not complete scheduled visits)
- If any clinical adverse event (AE), laboratory abnormality, or other medical condition or situation occurs such that continued participation in the study would not be in the best interest of the subject

Subjects who sign the informed consent form but do not receive the study intervention will be replaced and will not be counted against the enrollment total. A one-to-one replacement will occur. Every patient who does not receive the study intervention will be replaced with another participant.

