10.0 STUDY ASSESSMENT SCHEDULE AND PROCEDURES

10.1 Study Calendar

Procedure (Visit Window)	Visit 1 (V1) (Day 0)	F/U 1 ⁵ (Day 7-15)	Visit 2 (V2) (Day 28-65)	Visit 3 (V3) (V1 + 180 days +/- 30 days)
Informed Consent	X			
Demographics	Χ			
Concomitant Medications	X		Х	Х
Medical History ¹	Χ			
Inclusion/Exclusion Criteria	Х			
Blood draw (Serum & CMI)	X		X	Х
Standard of Care Recombinant COVID-19 Vaccine Booster	X			
7-Day Vaccine Diary ²	X			
SCAI, PDAI, or SCCAI Questionnaire ³	Х		Х	х
Adverse Event Monitoring	Х	Х	Х	Х
Telephone Contact ⁴		Χ		

Notes:

- 1. Baseline medical history included all IBD diagnoses or solid organ transplant diagnoses, medication history, and information in the source documents.
- 2. Dispense the 7-day Vaccine Diary at Visit 1 for subjects to complete at home.
- 3. SCAI, PDAI, or SCCAI will be administered based on IBD diagnosis at visits 1, 2, and 3.
- 4. Between Visit 1 and Visit 2, the study staff will attempt two phone contacts to assess AEs and remind them to complete vaccine diaries as well as to assist with subject retention.
- 5. Visits can be conducted via telephone calls. Patients who don't respond to survey will be emailed and receive a phone call reminding them to fill out diary.

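### SAEs are actively sought only by participant report, and the record search covers only acute rejection, so an SAE in anyone lost before V3 could be missing from the count out of 21

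*Combined protocol and SAP*

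**What the plan says.** - **Endpoint.** Section 6.3 summarises SAEs and fatal SAEs as a count and percentage, from the booster to study end. The success criterion is descriptive. The Synopsis gives 21 enrolled, and section 10.3 counts a person as enrolled only after consent and vaccination, so all 21 were vaccinated.
- **How SAEs are found.** Section 13.26: "SAE will be reviewed based on follow-up at V1, V2, V3, and vaccine diaries". Section 13.1, on contacts at FU1, V2 and V3: "Research coordinators will interview all participants at these visits and ask them about any AE since immunization". Section 13.23: "At each study visit, the investigator will inquire about the occurrence of AE/SAEs since the last visit". Section 10.1, note 4, adds: "Between Visit 1 and Visit 2, the study staff will attempt two phone contacts to assess AEs and remind them to complete vaccine diaries". The diary covers 7 days.
- **Collection period.** Section 13.23 records reportable events "with start dates occurring any time after the administration of the study drug through the 6 month follow-up visit".
- **Acute rejection.** Sections 6.5 and 10.4.2 combine a search of electronic medical records with asking the patient. Section 13.21 adds: "Episodes of acute rejection will be documented by chart review". Section 13.26 repeats this.
- **Missed visits.** Section 8.5 lets participants withdraw at any time and makes uncompleted visits a ground for withdrawal. The rule for missing safety data (sections 6.3 and 10.4.3) covers only the diary and the FU1 contact.

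**The concern.** Every active route to an SAE needs the participant to be alive, able and present. That fits poorly with an endpoint that includes fatal events, which the participant cannot report. A serious illness or death may also be the reason V3 was missed. The people whose status is unknown could then be the ones more likely to have had an event, and any error would run towards under-counting.

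Because the endpoint is descriptive, the count and percentage are themselves the result. Section 12.1 says the sample is large enough to estimate adverse event rates accurately, and that presupposes that events are found in everyone vaccinated. The site already uses a method that does not depend on attendance, but it prescribes that method for one outcome only.

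**Working it through.** The plan states no SAE rate, drop-out rate or precision target, and section 12.1 says no formal sample size was calculated. There is no planned figure to reproduce.

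**Step 1. Which routes reach a participant lost before V3?**

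| Route | Section | Reach |
|---|---|---|
| 7-day diary | 6.3, 13.26 | First week, self-completed |
| FU1 and phone contacts | 10.1, 13.1 | Only up to V2 |
| V2 interview | 13.1, 13.23 | Up to V2, if attended |
| V3 interview | 13.1, 13.23 | None, if V3 is missed |
| Participant contacts the team | 10.2 | Only if able and willing |
| Presentation for care | 13.23 | Only if study staff learn of it |
| Monitor review | 13.27 | Up to 20% of records: 0.20 × 21 = 4.2, about 4 participants; more if judged necessary |
| Record search | 6.5, 10.4.2, 13.21, 13.26 | Independent of attendance, but for acute rejection only |

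The last row is the only systematic route that does not depend on the participant, and it is not prescribed for deaths or hospitalisations.

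**Step 2. Does a missed V2 matter?** Section 13.1 has the V3 interview ask about any event since immunization. Someone who missed V2 but attended V3 is covered for the whole period. The exposed group is those who died, were incapacitated or were lost before V3.

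**Step 3. Size of one missed event.** 1/21 = 4.8%. Exact (Clopper-Pearson) 95% limits for x events in n = 21 are the 0.025 quantile of Beta(x, n − x + 1) and the 0.975 quantile of Beta(x + 1, n − x), with lower limit 0 when x = 0:

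| x/21 | Percentage | 95% CI |
|---|---|---|
| 0 | 0% | 0 to 16.1% |
| 1 | 4.8% | 0.1 to 23.8% |
| 2 | 9.5% | 1.2 to 30.4% |

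**Step 4. Range when k participants have unknown status.** The value of k is an assumption. With x events found, and ascertainment complete in everyone else, the true percentage lies between x/21 and (x + k)/21.

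- x = 0: the upper bound is 0%, 4.8%, 9.5%, 14.3% or 19.0% for k = 0, 1, 2, 3 or 4.
- x = 1, k = 2: 1/21 = 4.8%; 1/(21 − 2) = 5.3% if only those with known status are counted; (1 + 2)/21 = 14.3% at worst.

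**Step 5. Expected understatement.** Assume a six-month SAE risk p in those lost, with all their events missed. The expected shortfall with denominator 21 is p × k/21, and the chance that at least one of them had an SAE is 1 − (1 − p)^k.

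- p = 5%, k = 1: 0.05 × 1/21 = 0.24 points; chance 5%.
- p = 20%, k = 4: 0.20 × 4/21 = 3.81 points; chance 1 − 0.8^4 = 59%.

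Both p and k are assumptions. If the event itself causes the loss, p in this group is higher than in the rest.

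**The case against.** The strongest reply is that nobody is shown to have missed V3. The harm is hypothetical, any visit-based safety collection shares it, the endpoint is descriptive, and the intervals in step 3 overlap widely. All of that stands, and it sets the weight of the point: what is at risk is the reported count, not a test or a conclusion.

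Second, losses are tracked. Section 11.0 has the Data Management Center report compliance and drop-outs, with monthly status reports during recruitment and a six-monthly report that includes clinical and adverse events. This should show who is lost. It does not say how that person's SAE or vital status is then established.

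Third, section 12.2 promises a formal SAP before database lock, and denominators and unknown-status counts could be set there. That is fair for the reporting rule, so its absence here does not show that none will exist. An SAP cannot recover events that were never collected, however.

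Fourth, transplant recipients' records are already searched for rejection, so an admission or death could well be noticed. This is largely right, although staff are not told to record it. It narrows the point mainly to participants with IBD alone. The documents do not say how many of the 21 those are.

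Two stronger readings are tempting. A reader might infer that a missed V2 also loses events, or that the wording in section 13.23, which looks back only to the last visit, leaves a hole. The section 13.1 look-back to immunization closes it. A reader might also infer that the long interval between V2 and V3, with no scheduled contact, causes loss in itself. It does not when V3 is attended, so the length of that interval does not measure the gap.

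**Conclusion.** The point holds in limited form. Active SAE finding rests on participant report, the systematic record search is confined to acute rejection, and a fatal or incapacitating event before V3 could be found only through incidental routes. The SAE percentage could then be too low by 4.8 points for each participant missed.

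This rests on three things: the denominator is the 21 vaccinated participants; at least one of them did not complete V3; and that person had an SAE that the incidental routes did not pick up. The documents establish only the first. A reader might conclude that SAEs or deaths were in fact under-counted, but nothing in the documents shows a missed visit or a missed event, and the size of any error cannot be derived from them. If all 21 completed V3, the gap largely disappears.

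This is a cheap improvement worth considering, not a flaw that undermines the study's findings.

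**What to change.** In sections 6.3, 13.23 and 13.26, extend the existing electronic-record search to deaths and hospitalisations, including any hospitalisation for myocarditis or pericarditis.

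- **Who:** every vaccinated participant; at minimum, those without a completed V3.
- **Period:** from the booster to the actual V3 date or, where V3 was missed, to the close of its window (Day 180 + 30 = Day 210).
- **Limits:** stay within consent for anyone who withdrew. Do not use the search to reconstruct IBD flares, which are defined by questionnaire indices. The rejection search stays as it is.
- **Reporting:** give the SAE percentage together with the number of participants whose SAE and vital status at V3 is unknown.

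The search can be done retrospectively if follow-up has ended. It costs a short protocol clarification, a little chart time for at most 21 records at one centre, and a consent check for any withdrawals. Care outside the health system may still be missed, which is why the unknown-status count should be reported. If all 21 completed V3, stating so meets most of the need.
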